10.1.3 Vital Signs, Height and Weight

Vital signs will be collected (in seated position after 5 mins) at timepoints noted below:

Weight, blood pressure, heart rate, and temperature will be measured at Screening, Baseline, Week 1, Week 2, and Week 4.

Height will be measured at Screening only.

10.1.4 12-lead ECGs

12-lead ECGs will be performed as follows: Screening and Week 4.

ECGs will be performed on subjects after 5 minutes in the supine position. All ECG tracings and readouts will be reviewed by the central reader at the ECG laboratory.

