10.1.5 Laboratory Tests

All tests listed below will be performed as follows:

Screening, Baseline, and Week 4.

All tests listed below will be performed according to the Study Events Flow Chart unless otherwise noted. The collection of specimens will be in a non-fasting state (no food restrictions). In addition, laboratory safety tests may be performed at various unscheduled time points, if deemed necessary by the Investigator.

Hematology

- Hemoglobin
- Hematocrit
- Total and differential leukocyte count
- Red blood cell count with indices and morphology
- Platelet count

Serum Chemistry

- Blood Urea Nitrogen
- Bilirubin (total and direct)
- Alkaline phosphatase
- Aspartate aminotransferase
- Alanine aminotransferase
- Albumin
- Sodium
- Potassium
- Chloride
- Glucose
- Creatinine

Urinalysis

- pH
- Specific gravity
- Protein*
- Glucose
- Ketones
- Bilirubin
- Blood*
- Nitrite*
- Urobilinogen
- Leukocyte esterase*

Additional Tests

- Urine pregnancy test**
(for females of child bearing potential only)
- Serum pregnancy test (hCG)***
- FSH test, if indicated

* If urinalysis is positive for protein, blood, nitrite and/or leukocyte esterase, a microscopic examination (for red blood cells, white blood cells, bacteria, casts, and epithelial cells) will be performed.

** At baseline, Week 1, Week 2, and Week 4 for FOCBP only

*** At screening only

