10.5 Early Termination Visit

If a subject is withdrawn or wishes to exit the study, a termination visit will be scheduled. This visit should include the procedures and assessments that would be performed at the Week 4 visit (Day 29).

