## 5.4 Windowing Conventions

Statistical Windows have been proposed for early termination (ET) visits in this study:

	Day 1 (Baseline)	Day 8	Day 15	Day 29
--	------------------	-------	--------	--------

 INNOVADERM RESEARCH INC.	STATISTICAL ANALYSIS PLAN, Final V1.0Final 1.0
Protocol Number: AQR-151-212	Sponsor: Arcutis, Inc.

Visit	1	4	5	7
Statistical Window	Latest pre-dose measurement	[Day 2; day 11]	[Day 12 – Day 21]	[Day 22 – D32]

If there is more than one assessment for a given timepoint and analysis visit, the assessment closest to the target day will be considered. If there is more than one assessment with the same target date, then the scheduled assessment result will be considered.

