## 5.6 Handling of Retests, Unscheduled Visits, and Early Termination Data

When retests measurements are done, the retest measurement will be considered for the summary analysis. All data from retest visits will be listed.

Unscheduled measurements will not be summarized in by-visit summary tables or figures. However, they will be included in shift summary tables. All data from unscheduled visits will be listed.

Early Termination (ET) visit assessments will be re-mapped according to the windowing conventions in section 5.4.

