## 13.2 Clinical Laboratory

Descriptive statistics will be presented for data related to chemistry, hematology, and urinalysis. Change from baseline values will be presented for each post-baseline assessment. Frequencies and percentages for each result will be provided for qualitative urinalysis data.

Shift tables from baseline to the worst post-baseline assessment describing shifts to abnormality will be provided as well. Only subjects with a baseline result and a post-baseline result for the parameter will be considered.

Separate listings of all data for chemistry, hematology, urinalysis, and pregnancy tests will be provided.

Laboratory data will be presented in SI units.

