## 13.4 Electrocardiogram (ECG)

Descriptive statistics will be presented for data related to ECGs (heart rate, RR duration, PR interval, QRS interval, QT interval, QTcB interval, and QTcF interval). Change from baseline values will be presented for each post-baseline assessment.

Shift tables from baseline to the worst post-baseline assessment describing shifts to abnormality for investigator overall interpretation will be provided as well.

A listing of the ECG assessments will be provided.

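### Early-termination laboratory and ECG results from Days 2–21 are labelled Week 1 or Week 2, where neither test is scheduled, and so are absent from the Week 4 change-from-baseline summary

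*SAP*

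**What the plan says.** Protocol 10.5 gives a subject who leaves early a termination visit: "This visit should include the procedures and assessments that would be performed at the Week 4 visit (Day 29"). That visit therefore includes the laboratory panel and the ECG.

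The Protocol schedules those two tests sparsely. Section 10.1.4 says "12-lead ECGs will be performed as follows: Screening and Week 4". Section 10.1.5 sets the laboratory tests at "Screening, Baseline, and Week 4". The flow charts in Protocol section 5 and SAP Table 1 agree: neither test is marked at Day 8 or Day 15.

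SAP 5.4 opens with "Statistical Windows have been proposed for early termination (ET) visits in this study". It then assigns Days 2–11 to Day 8, Days 12–21 to Day 15 and Days 22–32 to Day 29. SAP 5.6 applies these windows to all ET assessments: "Early Termination (ET) visit assessments will be re-mapped according to the windowing conventions in section 5.4".

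On reporting, SAP 13.4 says of ECG that "Change from baseline values will be presented for each post-baseline assessment", and SAP 13.2 says the same of laboratory data. SAP 5.5 presents summaries by treatment and visit. SAP 13.2 adds, for laboratory data, "Shift tables from baseline to the worst post-baseline assessment describing shifts to abnormality will be provided as well". SAP 13.4 adds, for ECG, "Shift tables from baseline to the worst post-baseline assessment describing shifts to abnormality for investigator overall interpretation will be provided as well". Both sections also provide listings.

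**The concern.** The windows suit assessments made at all three post-dose visits, such as EASI, BSA, itch and vital signs. Applied to a test scheduled only at Week 4, they move an early leaver's result to a visit at which no other subject is due to have that test. There it has no group of subjects still on study to sit beside, and the Week 4 row describes only subjects assessed on Day 22 or later.

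SAP section 2 names change from baseline in laboratory results and in ECG as safety endpoints. Early leaving may be informative for them: Protocol 9.7 and 10.9 list adverse events and confirmed, drug-related Grade 3 laboratory abnormalities among the grounds for stopping. SAP 5.6 also keeps unscheduled measurements out of by-visit tables, so for an early leaver the ET value is normally the only post-dose laboratory or ECG value that can enter one. Because withdrawn subjects may be replaced (Protocol 9.8, SAP 3.4.2), the Week 4 n can look complete while these results sit elsewhere.

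**Working it through.** **Inputs.** ET content: Protocol 10.5. Test schedule: Protocol section 5, 10.1.4 and 10.1.5, and SAP Table 1. Windows: SAP 5.4. Sample size and dropout: Protocol 11.1.4 and SAP 5.1.

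**1. The plan's own figures.** For a two-sample t-test with difference 35, SD 40 and two-sided alpha 0.05/2 = 0.025 (Bonferroni, two comparisons), power is 81.5% at 27 per arm and 79.8% at 26. The stated 27 reproduces. Inflating for dropout gives 27/0.90 = 30 and 27/0.75 = 36, against the stated 30 and 35. The difference of one is immaterial here; only the dropout range bears on this point.

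**2. Where an ET result goes.** Take possible exit days 2 to 28:

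- Days 2–11 go to Week 1: 10 days, test not scheduled.
- Days 12–21 go to Week 2: 10 days, test not scheduled.
- Days 22–28 go to Week 4: 7 days, test scheduled.

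So 20/27 = 74% of exit days map away from Week 4, and 7/27 = 26% map to it. This counts days, not subjects.

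**3. What each planned output shows for an ET result on Days 2–21.**

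- Week 4 by-visit change summary: absent, for both tests.
- By-visit summary under the re-mapped label: read literally, present by arm in a Week 1 or Week 2 row made up of early leavers.
- Laboratory shift to worst post-baseline value: present, because it does not depend on the visit label.
- ECG shift to worst post-baseline value: present, but for overall interpretation only.
- Listings: present.

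For the numeric ECG measures (heart rate, RR, PR, QRS, QT, QTcB, QTcF), the by-visit table is the only planned summary. Heart rate taken as a vital sign is scheduled at every main visit and is not affected.

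**4. How many subjects.** Dropouts per arm = rate × n per arm, with dropout taken as equal across arms:

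- Low: 0.10 × 30 = 3.
- High: 0.25 × 35 = 8.75, about 9.
- Trial-wide: 0.10 × 90 = 9 to 0.25 × 105 = 26.25, about 26.

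The documents give neither exit timing nor the proportion who attend an ET visit. If all leave on Day 22 or later, or none attends, 0 are affected. If all leave before Day 22 and all attend, all 3–9 per arm are. As an illustration only, with exits uniform over Days 2–28 and full attendance, 9 × 20/27 = 6.7 to 26.25 × 20/27 = 19.4 subjects, about 7 to 19 across the trial, would be missing from the Week 4 row.

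**The case against.** The strongest reply is that this is a display convention. Labelling a Day 6 result by its actual study day is defensible, and pooling it with Day 29 values mixes exposure lengths. Safety is descriptive (SAP 13), so no test depends on the Week 4 mean. Subjects who stop because of adverse events are covered in the adverse-event summaries and listings (SAP 13.1). Table layouts are in a separate document (SAP section 5), so the exact rows of the laboratory and ECG tables cannot be seen here. All of this stands, and it keeps the point small. It does not remove it: the written rule takes these results out of the Week 4 summary, and for ECG intervals no worst-value table makes up for that.

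A reader might infer more, in two ways that the documents do not support.

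- That every early leaver drops out of Week 4. ET visits on Days 22–32 map to Day 29 and stay in.
- That early leavers' results are lost, or missing from any comparison between arms. Read literally, the SAP still tabulates them by arm under another visit label, includes them in both worst-value shift tables and lists them.

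Nor can the whole dropout range be read as the number affected. It is a planning allowance that includes late leavers and subjects who never attend an ET visit, and no windowing rule recovers a result that was not collected.

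**Conclusion.** The point holds in a limited form and is minor. By the stated rule, ET laboratory and ECG results from Days 2–21 are absent from the by-visit change summary at the one post-dose time point where these tests are scheduled. The gap is clearest for numeric ECG values. The affected number is 0–9 per arm. The upper end rests on the plan's 25% dropout at 35 per arm, equal dropout across arms, every exit before Day 22 and full ET attendance. The finding also assumes that SAP 5.6 is applied as written and that the separate table layouts do not already provide an end-of-treatment row. The primary analysis, the secondary analyses and all p-values are untouched.

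**What to change.** Add to SAP 5.4 or 5.6: *For laboratory tests and ECG, whose only scheduled post-baseline visit is Week 4, the Day 8 and Day 15 windows do not apply. ET results on any post-dose day are summarised in an end-of-treatment (Week 4/ET) row by arm, with the n contributed by ET shown, alongside the observed Week 4 row.*

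Physical examination need not be included, because the SAP plans no by-visit summary of it.

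The cost is one sentence and one extra row per table, with no new data collection. The downside is that the end-of-treatment row mixes exposure lengths. Showing the ET n and keeping the observed Week 4 row lets a reader see how much that matters.

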## 5.7 Software Version

All analyses will be performed using SAS® software Version 9.4 or higher.

 INNOVADERM RESEARCH INC.	STATISTICAL ANALYSIS PLAN, Final V1.0Final 1.0
Protocol Number: AQR-151-212	Sponsor: Arcutis, Inc.

## 6 STATISTICAL CONSIDERATIONS

---

### 6.1 Adjustments for Covariates

For the efficacy parameters analyzed using a mixed-effects model for repeated measures (MMRM), the corresponding baseline value and the stratification factor vIGA-AD score (“2” (mild) or “3” (moderate)) will be included as covariates in the statistical model.

### 6.2 Handling of Dropouts or Missing data

See [Appendix 2](#) for handling of completely or partially missing dates for prior and concomitant medications and adverse events.

The primary method of handling of missing data will be the MMRM method without explicit imputations for missing data. A sensitivity analysis will be carried out on the primary endpoint using the last observation carried forward (LOCF) as an imputation for missing data. Only post-baseline values will be carried forward.

For secondary endpoints involving proportions, missing data at any post-baseline assessment will be imputed using LOCF and they will then be determined as a responder or non-responder based on the LOCF value.

### 6.3 Interim Analysis and Data Monitoring

No interim analysis is planned for this study.

### 6.4 Multicenter Studies

This is a multicenter study. Since randomization is not stratified by site, subjects will be analysed as if from a single center (i.e. all sites are combined).

### 6.5 Statistical Tests

Unless otherwise specified, all statistical tests will be two-sided and will be performed with a significance level of 0.05. Confidence intervals (CIs) will be two-sided with 95% coverage.

### 6.6 Multiple Comparisons/Multiplicity

The statistical test for each ARQ-151 dose level for the primary endpoint of Eczema Area and Severity Index (EASI) will be two-sided and will be performed with a significance level of 0.05 using Dunnett’s method to control the overall alpha level.

 INNOVADERM RESEARCH INC.	STATISTICAL ANALYSIS PLAN, Final V1.0Final 1.0
Protocol Number: AQR-151-212	Sponsor: Arcutis, Inc.

No adjustments will be made to account for multiplicity in secondary and exploratory endpoints and multiple assessments through time in the same subjects. P-values presented for these endpoints will be nominal p-values.

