11.1.4 Determination of Sample Size

The sample size will be approximately 90 to 105 subjects. A subset of subjects enrolled under the previous amendment will receive serial PK sampling.

A sample size of 27 per arm will provide at least 80% power to detect a difference in the mean change from baseline in EASI Total Score of 35% at week 4 (for each ARQ-151-treated group versus vehicle-treated group), assuming a pooled standard deviation of 40%, with a two-sided $\alpha = 0.05$. This is based on a 2-sample t-test. This includes P value adjustment for multiplicity using Bonferroni correction. With a 10-25% dropout rate, the sample size for the study would be increased to 30-35 subjects per arm (90-105 subjects total). Change from baseline in EASI Total Score at week 4 is expected to provide more statistical power than percent change from baseline in Total EASI Score at this timepoint (which is a secondary endpoint) and has been chosen as the primary endpoint.

This sample size is considered adequate for PK and safety evaluation.

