### 3.5 Changes to the Analysis from the Protocol

The primary method of handling of missing data will be the MMRM method without explicit imputations for missing data as opposed to a multiple imputation technique.

The PHQ-8 scoring in the protocol describes "Severe Depression" as any score between 20 and 27. The PHQ-8 score has a maximum result of 24, The category has been corrected in [section 13.6](#) to a score between 20-24.

 INNOVADERM RESEARCH INC.	STATISTICAL ANALYSIS PLAN, Final V1.0Final 1.0
Protocol Number: AQR-151-212	Sponsor: Arcutis, Inc.

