## 5.1 Sample Size

There are approximately 90-105 subjects planned for this study. A subset of approximately 18 adults will receive serial PK sampling.

Approximately 30-35 subjects will receive ARQ-151 cream 0.05% QD; approximately 30-35 subjects will receive ARQ-151 cream 0.15% QD; approximately 30-35 subjects will receive vehicle QD.

A sample size of 27 per arm will provide at least 80% power to detect a difference in the mean change from baseline in EASI Total Score of 35% at week 4 (for each ARQ-151-treated group versus vehicle-treated group), assuming a pooled standard deviation (SD) of 40%, with a two-sided  $\alpha = 0.05$ . This is based on a 2-sample t-test. This includes P value adjustment for multiplicity using Bonferroni correction. With a 10-25% dropout rate, the sample size for the study would be increased to 30-35 subjects per arm (90-105 subjects total).

Change from baseline in EASI Total Score at week 4 is expected to provide more statistical power than percent change from baseline in EASI Total Score at this timepoint (which is a secondary endpoint) and has been chosen as the primary endpoint.

This sample size is considered adequate for PK and safety evaluation.

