### Primary Endpoint Analysis

The primary efficacy endpoint is change from baseline in EASI Total Score at Week 4.

The primary efficacy endpoint will be analyzed using a MMRM analysis on change-from-baseline EASI with subject as a random effect and vIGA-AD strata, visit, treatment group, and interaction term for treatment-by-visit as fixed effects and baseline EASI as a fixed covariate. An unstructured variance-covariance matrix will be used. The Kenward-Roger approximation will be used to estimate denominator degrees of freedom. The primary treatment comparisons will be the contrast between each dose of ARQ-151 with the Vehicle at Week 4.

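### SAP 6.6 does not state the form of Dunnett's test; the step-down form would add power for the second dose at the same family-wise error of 0.05

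*SAP*

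**What the plan says.** The primary family has two members. SAP 12.1 (Primary Endpoint Analysis) states: "The primary treatment comparisons will be the contrast between each dose of ARQ-151 with the Vehicle at Week 4". For these, SAP 6.6 says that each two-sided test "will be performed with a significance level of 0.05 using Dunnett’s method to control the overall alpha level". Neither section says whether the method is single-step (both contrasts against one fixed critical value) or step-down.

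The sample-size text names another method. Protocol 11.1.4 states: "A sample size of 27 per arm will provide at least 80% power" for a "difference in the mean change from baseline in EASI Total Score of 35% at week 4", "assuming a pooled standard deviation of 40" per cent, based on a two-sample t-test. SAP 5.1 repeats the calculation and adds, as the protocol does: "This includes P value adjustment for multiplicity using Bonferroni correction".

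The protocol's own analysis text (11.2.1) refers only to an appropriate contrast at Week 4 and names no multiplicity rule. SAP 3.5 lists two changes from the protocol. One corrects the PHQ-8 categories. The other concerns dropouts: "The primary method of handling of missing data will be the MMRM method without explicit imputations for missing data as opposed to a multiple imputation". Nothing in that section mentions the choice of Dunnett.

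**The concern.** If SAP 6.6 is read in the default way, each dose must clear the same adjusted threshold, whatever happens to the other dose. That is stricter than a family-wise rate of 0.05 requires. Once one dose has been declared different from vehicle, only one null hypothesis is left that could be wrongly rejected, and it can be tested at the full two-sided 0.05. The single-step form does not use this.

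What is at stake is the verdict on the second concentration. The study compares two concentrations with vehicle, and the sample size is justified by power for each of them. A second dose with an unadjusted p between about 0.027 and 0.05 would fail under single-step Dunnett and succeed under step-down.

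There is also a documentation gap. The SAP names Bonferroni in one section and Dunnett in another, and its list of changes does not connect them.

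**Working it through.** **Inputs.** Difference 35, SD 40, 27 per arm, two-sided 0.05 and Bonferroni for two comparisons (Protocol 11.1.4, SAP 5.1); 1:1:1 allocation (Protocol 9.3); two contrasts sharing the vehicle arm (SAP 12.1). The percent units are used as written, although the primary endpoint is absolute EASI change.

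**1. Reproduce the plan's 27.** Standardised effect d = 35/40 = 0.875. Power = P(|T| > t critical), where T is noncentral t with 2n − 2 degrees of freedom and noncentrality d·√(n/2). Per-dose alpha = 0.05/2 = 0.025.
- n = 27: noncentrality 0.875 × √13.5 = 3.215; power 81.5%.
- n = 26: noncentrality 0.875 × √13 = 3.155; power 79.8%.

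So 27 is the Bonferroni figure, and it reproduces.

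**2. Dunnett threshold.** With equal arms, the covariance of the two contrasts is σ²/n and each variance is 2σ²/n, so their correlation is 0.5. Solving P(max(|T1|, |T2|) > c) = 0.05 for the bivariate t with 3 × (27 − 1) = 78 degrees of freedom gives c = 2.253, a per-dose two-sided p of 0.0271. At that level the t-test in step 1 has 82.4% power with 27 per arm and would need 26. The claim of at least 80% therefore holds under either method.

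**3. Step-down rule and its error.** Test the larger |t| against c. If it is significant, test the other contrast at two-sided 0.05.
- Both nulls true: any rejection needs the larger |t| to exceed c, so the error is that of Dunnett. Simulated: 4.99% for both forms (Bonferroni 4.63%).
- One null true: rejecting it needs at least its own p below 0.05. With the other dose at the planned effect, the null dose is rejected in 2.7% of trials under single-step and 4.4% under step-down, still below 5%.

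**4. Power.** 1,000,000 simulated three-arm trials, pooled-variance t tests, both doses at 35/40:

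| n per arm | Rule | A given dose | Both doses | At least one |
|---|---|---|---|---|
| 27 | Bonferroni | 82.2% | 71.9% | 92.4% |
| 27 | Single-step Dunnett | 83.0% | 73.1% | 93.0% |
| 27 | Step-down Dunnett | 86.9% | 80.9% | 93.0% |
| 30 | Single-step Dunnett | 87.1% | 78.9% | 95.2% |
| 30 | Step-down Dunnett | 90.4% | 85.6% | 95.2% |
| 35 | Single-step Dunnett | 92.0% | 86.4% | 97.6% |
| 35 | Step-down Dunnett | 94.4% | 91.3% | 97.6% |

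Bonferroni shows 82.2% here and 81.5% in step 1 because the simulation pools the variance over three arms.

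**5. Consistency check.** The two Dunnett forms differ only in trials where one dose passes and the other has p between 0.0271 and 0.05. Each such trial adds one rejection, and with equal effects these are shared equally between the doses. The both-dose gain of 80.9 − 73.1 = 7.8 points should therefore give 7.8/2 = 3.9 points per dose, and 86.9 − 83.0 = 3.9.

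**6. Unequal effects** (assumed; not in the documents). At 27 per arm with one dose at 35, power for the weaker dose under single-step and step-down is 51.9% and 60.4% if its true difference is 25, and 26.5% and 34.8% if it is 17.5.

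**The case against.** Single-step Dunnett is a legitimate choice. It controls the family-wise error and has matching simultaneous intervals, and the per-dose power target is already met. The documents do not define success as winning on both doses. If proof of concept means that at least one concentration works, step-down adds nothing. The both-dose gain also shrinks as power rises: 7.8 points at 27 per arm, 6.7 at 30 and 4.9 at 35. The plan expects absolute change to be a more powerful endpoint than percent change, which would shrink it further. All of this stands, and it makes the point an improvement and not the correction of an error.

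The loss of matching intervals weighs less. SAP 6.5 sets ordinary two-sided 95% intervals and SAP 6.6 promises no simultaneous ones, so the plan would lose nothing it commits to.

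Three stronger readings are tempting, and the documents do not support them:
- *The primary tests carry two competing decision rules, so a p of 0.026 is both a failure and a success.* Bonferroni appears only in the sample-size paragraphs, as part of the power calculation. Protocol 11.1 describes its methods as a summary of the fuller SAP, and SAP 6.6 is the only place that gives a rule for the tests.
- *The stated power is wrong because it belongs to another test.* Planning with the slightly stricter threshold is conservative, and the claim holds at either level (81.5% and 82.4%).
- *The plan's methods waste power in general.* For at least one dose, step-down gains nothing over single-step Dunnett, and Bonferroni loses only about half a point (92.4% against 93.0%).

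Finally, single-step is an inference from common usage; SAP 6.6 does not say it.

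**Conclusion.** The planned primary test is valid, but its form is unstated, and the default form gives up power for the second dose that can be had at the same family-wise error. With 27 evaluable per arm and both doses at the planned effect, the gain is about 4 points per dose (83% to 87%) and about 8 points for both doses (73% to 81%). For both doses it is 79% to 86% at 30 per arm and 86% to 91% at 35. Power for at least one dose is unchanged.

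These figures assume complete data, equal arms, a common variance, a t model and the plan's 35 and 40 taken at face value. The planned MMRM with missing data will differ somewhat. The ordering of the two forms does not depend on these inputs, because step-down rejects whenever single-step does.

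The Bonferroni wording is secondary housekeeping: a conservative planning assumption whose replacement by Dunnett was not recorded.

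**What to change.** Before unblinding:

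1. **SAP 6.6.** Specify step-down Dunnett for the two Week 4 contrasts. Test the larger |t| at the two-sided Dunnett 0.05 critical value; if it is significant, test the other contrast at two-sided 0.05; otherwise stop. For reporting, the adjusted p-value of the first contrast is its Dunnett p, and that of the second is the larger of the first contrast's Dunnett p and its own unadjusted p. If the team prefers single-step, the section should say so.
2. **SAP 5.1.** Replace the Bonferroni sentence with the method in SAP 6.6, or say that Bonferroni was used as a conservative planning approximation. If step-down is adopted, the power on the stated inputs at 27 evaluable per arm is about 87% per dose when both doses have the planned effect. It is about 83% for a dose at the planned effect when the other dose has none.
3. **SAP 3.5.** Add the move from Bonferroni in the planning text to Dunnett in the analysis.

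The cost is SAP wording and a few lines of code; no more subjects and no protocol amendment. The drawback should be stated in the SAP: a step-down test has no simple matching simultaneous interval. If single-step Dunnett intervals are shown, one may include zero for a dose that is significant only at the second step. The ordinary 95% intervals of SAP 6.5 do not have this problem, because a dose rejected at the second step has an unadjusted p below 0.05.
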